# LAY SUMMARY

Men who have sex with men (MSM) and Transgender women (TGW) who have sex with men continue to be disproportionately affected by HIV. Over 60% of new HIV infections in the US occur among MSM. The majority of HIV infections among MSM and

TGW occur through exposure to the rectal mucosa during receptive anal intercourse (RAI). Pre-exposure prophylaxis (PrEP) is a new HIV prevention method that is recommended by CDC and WHO for MSM at risk of HIV infection. PrEP entails taking an anti-HIV medication (Truvada®; tenofovir/emtricitabine) on a daily basis to prevent HIV infection. However, current tenofovir- based regimens have shown to have side effects that researchers are hoping to reduce in newly developed anti-HIV agents. This study is designed to examine the ability of these new agents to penetrate mucosal tissues and potentially prevent HIV infection during RAI exposure for MSM and TGW.

For this protocol, we will recruit HIV-negative MSM and TGW who are not on hormone therapy aged 18-49 and who are willing to adhere to study procedures. There will be 3 phases, with 2 study visits for phase I, 3 study visits for phase II, and 4 study visits for phase III that will be conducted over a maximum period of 12 weeks. Participants are allowed to participate in more than one phase if a recovery or washout period occurs 8 weeks in between each phase. The first visit for all phases (phase I, phase II, and phase III) will be a screening visit where eligibility is determined, written informed consent is obtained, screening tests are performed, and men will be randomized to one of two study groups: 1. Use of oral Truvada®; or 2. Use of oral Genvoya®. During the second study visit (visit 2), men in phase I will not receive product, but will come in for blood work, urine sample, 2 pre-wet penile swabs, urethral swab, rectal swab, and rectal biopsy sampling. Participants who are in phase II will receive a single dose of the study product during visit 2, 1-6 weeks after the screening visit. MSM will return 4 to 6 hours after taking the drug for a urine sample. We will then collect 4 tablespoons of blood from the participants arm, in addition to, 2 pre-wet penile swabs, and a urethral swab. The third study visit will occur 24 hours from dosing time for MSM in phase II. Men will undergo a blood draw, urine sample, penile, urethral, and rectal swab, and rigid sigmoidoscopy for collection of rectal secretions and biopsies. Participants in phase III at study visit 2 will receive a 10-day supply of the study drug and will be instructed to take it for 10 consecutive days. For visit 3 in phase III, participants will return for a blood draw, urine collection, 2 pre-wet penile swabs, and a urethral swab to examine drug levels after 3-5 days of taking study drug. They will then return 10 days from dosage for visit 4, where blood, urine, penile, urethral, and rectal swabs will be collected, and rectal biopsy sampling will occur. All specimens will be transported directly to the laboratory of [name] at CDC where multiple immune assays are planned to determine the ability of these agents to penetrate mucosal tissues and potentially prevent HIV infection during RAI exposure.

# PROJECT DESCRIPTION

**Public Health Relevance:** Information about new anti-HIV agents and how they penetrate through mucosal tissues will better inform scientists about the potential of new agents to be used for pre-exposure prophylaxis (PrEP).

**Goal**: To compare the body compartment pharmacokinetics and mucosal inflammatory effects of Truvada® vs. Genvoya®.

Version 6 04/21/17

# STUDY POPULATION

A total of 90 HIV-negative MSM aged 18-49 will be recruited from existing Emory University study databases of MSM who have agreed to future contact about research opportunities. We will also recruit men from community engagements events conducted by Hope Clinic recruiters, from print and on-line advertisements, and from social media advertisements. Research recruiters at the Hope Clinic and the Rollins School of Public Health are experienced in recruiting this population for research studies, including those with rectal biopsies, and do not anticipate problems. [name] is has conducted 2 similar studies before and does not anticipate any problems with recruiting the target population. Based on our previous studies, we expect approximately 20% of men will not complete all study visits, therefore the sample size of 90 men will likely result in study completion for 72 men.

# **INCLUSION CRITERIA FOR MSM**

- 1) HIV-negative man who reports receptive anal sex with another man in the last 6 months
- 2) Male to female transgender women who have sex with men who report receptive anal intercourse with another man in the last 6 months and are not currently taking hormonal therapy or plan to take hormonal therapy for the duration of the study
- 3) Aged 18-49 years
- 4) Not currently taking PrEP and no plans to initiate during study
- 5) Able to provide informed consent in English
- 6) No plans for relocation in the next 3 months
- 7) Willing to undergo peripheral blood and rectal biopsy sampling
- 8) Willing to use study products as directed
- 9) Willing to abstain from receptive anal intercourse 3 days prior to starting study product and for the duration of the study and for 7 days after any rectal biopsy procedure.

# EXCLUSION CRITERIA

- History of inflammatory bowel disease or other inflammatory, infiltrative, infectious or vascular condition involving the lower gastrointestinal tract that, in the judgment of the investigators, may be worsened by study procedures or may significantly distort the anatomy of the distal large bowel
- 2) Significant laboratory abnormalities at baseline visit, including but not limited to:
  - a) Hgb  $\leq$  10 g/dL
  - b) PTT > 1.5x ULN or INR > 1.5x ULN
  - c) Platelet count <100,000
  - d) Creatinine clearance <60

- Any known medical condition that, in the judgment of the investigators, increases the risk of local or systemic complications of endoscopic procedures or pelvic examination, including but not limited to:
  - a) Uncontrolled or severe cardiac arrhythmia
  - b) Recent major abdominal, cardiothoracic, or neurological surgery
  - c) History of uncontrolled bleeding diathesis
  - d) History of colonic, rectal, or vaginal perforation, fistula, or malignancy
  - e) History or evidence on clinical examination of ulcerative, suppurative, or proliferative lesions of the anorectal or vaginal mucosa, or untreated sexually transmitted disease with mucosal involvement
- 4) Continued need for, or use during the 14 days prior to enrollment, of the following medications:
  - a) Aspirin or more than 4 doses of NSAIDs
  - b) Warfarin, heparin (low-molecular weight or unfractionated), platelet aggregation inhibitors, or fibrinolytic agents
  - c) Any form of rectally administered agent besides products lubricants or douching used for sexual intercourse
- 5) Continued need for, or use during the 90 days prior to enrollment, of the following medications:
  - a) Systemic immunomodulatory agents
  - b) Supraphysiologic doses of steroids
  - c) Experimental medications, vaccines, or biologicals
- 6) Intent to use HIV antiretroviral pre-exposure prophylaxis (PrEP) during the study, outside of the study procedures
- 7) Symptoms of an untreated rectal sexually transmitted infection (e.g. rectal pain, discharge, bleeding, etc.)
- 8) Current use of hormonal therapy
- 9) Any other clinical condition or prior therapy that, in the opinion of the investigator, would make the patient unsuitable for the study or unable to comply with the study requirements.

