men will be screened for eligibility and will undergo the informed consent process. Once informed consent is signed, a physical examination will be performed, rapid HIV testing, phlebotomy for screening labs, and randomization will occur. During study visit 2 (time 1-6 weeks after study visit 1), men will be dispensed and instructed to take either Truvada® or Genvoya® for 10 days. After 3 to 5 consecutive days of dosing, participants will return for visit 3 where a urethral and penile swabs specimen, blood work, and a urine specimens will be obtained. During study visit 4 (time 10 days of consecutive drug dosing), men will return for repeat phlebotomy, urethral and penile swabs, collection of urine and rectal secretions, and rectal biopsy. After collection, biologic specimens will be immediately transported by courier to CDC (laboratory of [name]) for processing. Specimens will be processed immediately for ex vivo laboratory assays that will include Truvada® and/or Genvoya® drug concentrations, inflammatory cytokine levels, HIV target cell measurement and characterization by flow cytometry, and in vitro HIV infection assays. Comparison of assay results between the 2 study arms will help in determining the ability of the new formulated anti-HIV drug to penetrate different body compartments at the site of possible HIV exposure.

Participants may participate in more than one phase; however, at least 8 weeks must lapse after completion of 1 study phase before entry into another. Men who participate in more than one phase will not be consented again and do not have to repeat the screening visit (visit 1) when starting another phase; they will begin the new phase at visit 2.

Duration: The duration of this study is 3 years. Participants will be considered 'on-study' for no more than 12 weeks.

Sample size: For this protocol we will recruit 90 HIV-negative MSM or transgender women who are not taking hormone therapy who meet eligibility criteria outlined in the protocol.

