# Visit 1

# Phase I, II, and III

During the screening visit, eligible MSM will provide written informed consent after all their questions are answered in a private exam room at the Hope Clinic. Subjects will also receive an approved HIPAA statement and will be informed about the way their protected health information will be used and stored. Copies of the consent/HIPAA form for this project will not be placed in individuals' medical records since this study collects sensitive information such as HIV status and sexual orientation.

After provision of informed consent, a medical history and physical examination will be conducted by the PI to evaluate for exclusion criteria. A rapid HIV test with finger stick whole blood (Determine or other CLIA waved product) will be performed by the PI or study coordinator who will be certified in HIV counseling and testing to confirm eligibility. Peripheral blood will be drawn for a complete blood count, creatinine, and coagulation tests.

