# Visit 2

Version 6 04/21/17

Participants will be randomized to one of two study arms:

Arm 1. Use of Truvada®

Arm 2. Use of Genvoya®

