# Phase I

10 participants (5 in each study arm) will be enrolled in study phase 1.

Study visit 2 will occur 1-6 weeks after the screening visit. During visit 2, we will draw 4 tablespoons of blood from the participants arm. A urine sample as well as penile and urethral swabs will be collected from participants. These samples will be used at CDC to develop an assay to detect Truvada® and Genvoya® in the body compartments. All specimens will be coded with a unique numeric identifier such that the CDC laboratories that receive the specimens will be unable to link them back to the study participants. Finally, rigid sigmoidoscopy (described further below) will be performed and, rectal secretions will be collected with Dacron swabs, and 8-12 rectal biopsies will be collected. A rectal swab will be collected for testing for gonorrhea and chlamydia to be performed by CDC. If positive for gonorrhea or chlamydia, men will be referred for care at their private physician's office, the health department, or AID Atlanta for treatment. All men will be instructed to place nothing in the rectum and to abstain from sex for 7 days after the procedure to allow the mucosa to heal.

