# Phase III

40 participants (20 in each study arm) will be enrolled in study phase 2.

Study visit 2 will occur 1-6 weeks after the screening visit. During visit 2, the study group assignment will be reviewed and participants will be provided with a 10 day supply of Truvada® or Genvoya®. Drug will be dispensed through the Emory Investigational Drug Service. Depending on the study arm they were assigned to, MSM will be dispensed 10 days of Truvada® or Genvoya® and instructed on dosing for 10 consecutive days prior to their scheduled study visit 4. MSM will be requested to abstain from receptive anal intercourse while on study product. Participants will be scheduled to return for their third study visit after taking the study product for 3-5 consecutive days.

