# Visit 3

# Phase II

Study visit 3 will occur 24 hours after they received their study product during visit 2. During visit 3, we will draw 4 tablespoons of blood from the participants arm. A urine sample as well as penile and urethral swabs will be collected from participants. These samples will be used at CDC to develop an assay to detect Truvada® and Genvoya® in the body compartments. All specimens will be coded with a unique numeric identifier such that the CDC laboratories that receive the specimens will be unable to link them back to the study participants. Finally, rigid sigmoidoscopy will be performed and, rectal secretions will be collected with Dacron swabs, and 8-12 rectal biopsies will be collected. A rectal swab will be collected for testing for gonorrhea and chlamydia to be performed by CDC. If positive for gonorrhea or chlamydia, men will be referred for care at their private physician's office, the health department, or AID Atlanta for treatment. All men will be instructed to place nothing in the rectum and to abstain from sex for 7 days after the procedure to allow the mucosa to heal.

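### The 14-day bar on bleeding-risk drugs is counted back from an undefined enrollment rather than from the biopsy, leaving 9 to 14 of the 14 days before a Phase III biopsy uncovered

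*Protocol*

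**What the plan says.** Criterion 4 (Protocol, EXCLUSION CRITERIA) reads "Continued need for, or use during the 14 days prior to enrollment, of the following medications". The list is aspirin or more than four NSAID doses; warfarin, heparin, antiplatelet and fibrinolytic agents; and rectal agents other than lubricants or douching for sex.

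Enrollment is not tied to a visit. The adverse event section uses it as a starting point without defining it, and the other signals conflict:

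- **Visit 1.** The Lay Summary says that at the screening visit "screening tests are performed, and men will be randomized to one of two study groups", and the Abstract agrees. For Phase III, the Visit 2 text treats allocation as already made: "the study group assignment will be reviewed and participants will be provided with a 10 day supply".
- **Visit 2.** The Visit 2 section opens with "Participants will be randomized to one of two study arms", and the enrollment sentences sit there too, for example "10 participants (5 in each study arm) will be enrolled in study phase 1".

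Visit 2 falls 1-6 weeks after screening. The 8-12 biopsies are taken at visit 2 in Phase I and at visit 3 in Phase II ("Study visit 3 will occur 24 hours after they received their study product during visit 2"). In Phase III they are taken at visit 4, after 10 days of dosing.

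The visible check of exclusions is at visit 1, where "a medical history and physical examination will be conducted by the PI to evaluate for exclusion criteria". Participants who enter a further phase, at least 8 weeks later, "do not have to repeat the screening visit (visit 1) when starting another phase; they will begin the new phase at visit 2".

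**The concern.** Aspirin, NSAIDs, anticoagulants and antiplatelet agents matter here mainly because of bleeding when the biopsies are taken. The protocol does not state the purpose of criterion 4, so this is an inference. It is a fair one for those drugs, and less clear for rectal agents, which may be listed to protect the mucosal measurements. On either purpose the relevant date is the biopsy, but the rule is attached to another date.

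Nothing in the visit, biopsy or risk text bars these drugs between enrollment and biopsy, or has staff ask about them again. The later checks that are named concern HIV risk and symptoms, serious adverse events and unanticipated problems. As written, a Phase III participant could take aspirin up to the day of biopsy without breaching criterion 4. At stake is an avoidable, probably small, bleeding risk in an elective research procedure that brings participants no direct benefit.

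**Working it through.** The protocol gives no coverage figure of its own, so there is none to reproduce.

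**Inputs.** Visit 1 is day 0, and visit 2 falls on days 7-42 (1-6 weeks). The biopsy is at visit 2 + 0 days (Phase I), + 1 (Phase II), or + 9 to + 10 (Phase III). The Phase III offset assumes dosing starts at visit 2: 9 if the biopsy is on the day of the tenth dose, 10 if it is ten days after visit 2.

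**Formula.** Days of the 14 before biopsy that lie inside the look-back = max(0, 14 − (biopsy day − enrollment day)).

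| Phase | Biopsy day | Covered if enrollment = visit 1 (best case) | Covered if enrollment = visit 2 | Uncovered if enrollment = visit 2 |
|---|---|---|---|---|
| I | 7-42 | 14 − 7 = 7 | 14 − 0 = 14 | 0 |
| II | 8-43 | 14 − 8 = 6 | 14 − 1 = 13 | 1 |
| III | 16-52 | max(0, 14 − 16) = 0 | 14 − 10 = 4 to 14 − 9 = 5 | 9-10 |

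Under the visit 1 reading, coverage is 0 in every phase once visit 2 is 14 or more days after screening.

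**Repeat participants.** The earliest Phase I biopsy is day 7, and 7 + 56 = 63 is the earliest repeat visit 2. A Phase II biopsy then falls on day 64 and a Phase III biopsy on day 72-73. Coverage counted from the original visit 1 is 0. If enrollment is renewed at each visit 2, the last columns apply, but no visible step asks the question.

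**How many.** Phase III is 40 of 90 planned. If the 20% loss in STUDY POPULATION applies equally, 40 × 0.8 = 32 complete. Per arm in Phase II or III, 20 × 0.8 = 16, so one missed biopsy is 1/16 = 6.25%.

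**Ceiling on risk.** The protocol reports more than 200 similar procedures with no complications. Taking 0 in 200, the one-sided 95% upper limit is 1 − 0.05^(1/200) = 1.49% per procedure. This bounds any complication, and the part due to these drugs would be smaller.

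**Room to reschedule.** Fourteen clean days require biopsy day ≥ last use + 15. Visit 2 must then be at least 15 (Phase I), 14 (Phase II) or 5-6 (Phase III) days after last use. With visit 2 no later than day 42, the latest use that can be accommodated is day 27, 28 or 36-37. The latest first-phase biopsy, day 52, is inside the 12-week limit (day 84).

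For repeat participants that limit can bind if it runs from first screening. A Phase I biopsy on day 14 puts the repeat visit 2 at day 70 or later. Use on day 70 moves the biopsy to day 70 + 15 = 85, past day 84.

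**The case against.** The strongest case on the other side is that anchoring an eligibility rule to enrollment is ordinary drafting. Advice on drugs to avoid before a procedure would normally sit in the consent form, the visit schedule or the CRFs. The consent pages and Figure 1 are not available, and the confidentiality section says the CRFs collect clinical data at rectal biopsy visits. Reminder contacts support adherence, the contingency visit allows rescheduling, and exclusion 9 gives the investigator discretion. The criterion itself tolerates up to four NSAID doses, so it was never strict for that class.

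The safety record also points to little at stake. Besides the 200-plus procedures, the protocol cites 64 research sigmoidoscopies with a mean of 25 biopsies and no major complication; 13 subjects had minor symptoms. Each participant is contacted 24-48 hours after biopsy.

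Much of this stands. Unseen text may partly close the gap. The documents give no rate of aspirin or NSAID use and no estimate of its effect on bleeding from these biopsies. What does not stand is reliance on the adherence contacts, rescheduling or discretion. No visible rule on these drugs applies after enrollment, and discretion works only if someone asks.

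A reader might infer that people on warfarin or daily aspirin could be biopsied unnoticed. The documents do not support that: the continued-need limb and the screening PTT, INR and platelet limits are there to catch chronic users. A reader might also infer that any late use should force the biopsy to be omitted. That is not supported either, because it would give up rectal tissue central to the study from someone already dosed, for a risk that appears small.

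**Conclusion.** The point holds as a cheap safety improvement. Criterion 4 misses the biopsy in Phase III whichever visit is enrollment: 9-10 of the 14 days are uncovered under the visit 2 reading, and all 14 under the visit 1 reading. Phases I and II have a material gap only under the visit 1 reading. The exposure is new or intermittent use after screening, mainly over-the-counter aspirin or NSAIDs. Repeat participants are not visibly asked again.

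The day counts measure look-back, not risk. A reader might take them to show substantial bleeding danger or a threat to the results. The documents show neither: absolute risk is low, and the SAP's comparison of drug levels is unaffected.

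The conclusion assumes that Phase III dosing starts at visit 2 and that the unavailable consent, Figure 1 and CRF text does not already restrict or ask about these drugs. If it does, what remains is to define enrollment and align the criterion.

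**What to change.** 1. Define enrollment as a named visit.
2. Reword criterion 4 so that the 14 days run back from enrollment or from any rectal biopsy, keeping the four-dose NSAID allowance.
3. Tell participants to avoid these drugs until after the biopsy: at visit 1 (or when a repeat phase is scheduled), in the reminder contacts already planned, and at Phase III visit 3.
4. Ask about them at visit 2 before dosing, and on arrival at each biopsy visit.
5. If use is found at or before visit 2, reschedule within the visit window and the 12-week on-study limit.
6. If use is found only at a Phase II or III biopsy visit, where timing is fixed by dosing, record it. Let the clinician performing the biopsy decide whether to proceed, take fewer biopsies or omit them. Omission should not be mandatory.

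The cost is a short amendment, one instruction, one CRF question per relevant visit, occasional rescheduled visits and a rare missed biopsy. Each missed biopsy is 1 of about 16 expected per arm in Phase II or III if the 20% loss applies equally. Asking before dosing lets most cases be rescheduled. Some late use, and some repeat participants near the 12-week limit, could not be accommodated.

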# Phase II

40 participants (20 in each study arm) will be enrolled in study phase 2.

Study visit 2 will occur 1-6 weeks after the screening visit. During visit 2, the study group assignment will be reviewed and participants will be provided with a single dose of Truvada® or Genvoya®. Drug will be dispensed through the Emory Investigational Drug Service. Depending on the study arm they were assigned to, MSM will be dispensed 1 day of Truvada® or Genvoya® and instructed on dosing for that day. Four to six hours after the drug is taken, a urine sample, 4 tablespoons of blood will be drawn from the participants arm, as well as, penile and urethral swabs will be collected from participants. These sample will be used at CDC to develop an assay to detect Truvada® and Genvoya® in the body. All specimens will be coded with a unique numeric identifier such that the CDC laboratories that receive the specimens will be unable to link them back to the study participants. Participants will be requested to abstain from receptive anal intercourse 3 days prior to study visit 2 and while taking study product.

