# Rectal biopsy procedures

[name] or [name] FNP will be performing all rectal biopsies utilizing a disposable rigid sigmoidoscope, light source, and jumbo biopsy forceps. [name] was trained in office based rectal biopsy procedures by [name], an experienced gastroenterologist at Emory University, and [name] trained [name]. All biopsy procedures will be performed in an examination room at the Hope Clinic with assistance from the project coordinator or clinical research nurse. Similar procedures have been performed by [name] or [name] >200 times for other research protocols with no complications. Briefly, without the administration of any previous enemas or other preparation, 8-12 adequate ~1.0 mm thick biopsy specimens will be taken from normal-appearing rectal mucosa 10 cm above the external anal aperture using a rigid sigmoidoscope and flexible sigmoidoscopic forceps mounted on a semi-flexible rod. All biopsy specimens will be coded with a unique numeric identifier such that the CDC laboratories that receive the specimens will be unable to link them back to

the study participants. Specimens will be transported directly to CDC after the study visit.

Twenty-four to forty-eight hours after the procedure, study personnel will contact the subjects who donated rectal biopsy samples and inquire about symptoms, complications, or adverse events related to study procedures. Subjects who report symptoms suggestive of any significant complications will receive advice on seeking care, and will be given referrals to appropriate healthcare professionals as needed. This follow-up may be completed over the phone or through electronic communication.

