Acquisition of HIV drug resistance is a theoretic concern for those taking Truvada® or Genvoya® for PrEP. However, clinical trials of Truvada® for PrEP have shown this to be a very rare event except in those who were 'acutely' infected with HIV at the time of study enrollment. In the iPrex study, there was no drug resistant virus detected in 100 MSM who became infected after enrollment. Of the ten men who were identified retrospectively to be acutely infected with HIV at enrollment, drug resistance was detected in 2/2 of men in the active drug arm and 1/8 of men in the placebo arm^6. For this protocol, we will test men for HIV at study entry and monitor clinically for high-risk behavior or any signs of acute HIV infection at study visits. If high risk behavior (e.g. unprotected anal intercourse with a man of unknown HIV status) or symptoms of acute HIV infection are reported, and HIV antibody test will be repeated and the participant will be counseled about the need for any follow-up testing. Clinical signs and symptoms of acute HIV infection that will be queried include: fever, fatigue, malaise, skin rash, swollen glands, oral/genital ulcers, myalgia/arthralgia. [name] will review all reports of clinical signs/symptoms to determine appropriate follow-up and linkage to care as necessary. If a diagnosis of acute HIV infection is thought to be possible or determined by repeat HIV testing, the participant will be discontinued from the study.. For this protocol, we will test men for HIV at study entry and monitor clinically for high-risk behavior or any signs of acute HIV infection at study visits.

Men will be asked to abstain from receptive anal intercourse while using drug during the study protocol in order to limit additional exposures (e.g. semen, douching, additional

Version 6 04/21/17

lubricants) to the rectal mucosa. Men taking Truvada® or Genvoya® will be counseled that they should not expect to achieve protection from HIV infection by taking drug during this study, as they will be provided a limited supply. All men included in the study that have an interest in taking PrEP for HIV prevention, will be referred to an area PrEP provider at the termination of the study. The Hope Clinic has compiled a resource sheet of area providers that will be distributed to interested participants.

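### The protocol wants douching and lubricant exposure of the rectum limited, but no participant instruction covers non-sexual rinsing or rectal products before the biopsy visit, and no item recording last use is named

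*Protocol*

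**What the plan says.** **Aim.** The Protocol's risk section (text following Risk of Genvoya®) asks men to avoid receptive anal intercourse while using drug "in order to limit additional exposures (e.g. semen, douching, additional"; the sentence goes on to name lubricants. Rectal biopsy procedures has specimens taken "without the administration of any previous enemas or other preparation".

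**Restrictions on participants.**
- Inclusion criterion 9: "Willing to abstain from receptive anal intercourse 3 days prior to starting study product and for the duration of the study". It adds a further week of abstinence following each biopsy.
- Study visits, Phase II, Visit 2: "Participants will be requested to abstain from receptive anal intercourse 3 days prior to study visit 2 and while taking study product".
- Study visits, Phase III, Visits 2 and 3: "MSM will be requested to abstain from receptive anal intercourse while on study product".
- The biopsy visits (Phase I Visit 2, Phase II Visit 3, Phase III Visit 4) tell men to insert nothing rectally, but only for the 7 days after the procedure.

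**Entry rule.** Exclusion 4 opens with "Continued need for, or use during the 14 days prior to enrollment, of the following medications", and item (c) reads "Any form of rectally administered agent besides products lubricants or douching used for sexual intercourse".

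**Data capture.** Subject Privacy and Data Confidentiality describes behavioral data at study entry and further clinical data at the study visit. The SAP lists behavioral data and counts the rectal biopsy visits among its sources. Neither names rectal rinsing, lubricant use or time since last use, and the SAP has no rule for handling such exposure.

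**The concern.** The protocol treats douching and lubricant as exposures that can disturb the rectal mucosa, yet its only instruction to participants before biopsy concerns intercourse. A man could keep to that instruction fully and still rinse or use a rectal product before a scheduled sigmoidoscopy. The no-enema wording describes what the clinic does and does not clearly bind what he does at home.

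The Goal is to compare compartment pharmacokinetics and mucosal inflammatory effects. Rectal secretions and biopsies are collected at one visit per phase, so a disturbed sample has no repeat within the phase. The Abstract gives the Phase I biopsy the role of establishing baseline values. Men in Phase I have no study drug on board, so what is at stake there is the inflammation baseline. In Phases II and III drug levels are exposed as well. If last use is not recorded, an analyst cannot separate affected samples afterwards.

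**Working it through.** The plan states no figure on this point. The check is a comparison of time windows, followed by an illustration on assumed inputs.

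**1. Does the exclusion 4(c) window reach the biopsy?** It covers the 14 days before enrollment, or continued need. The visit schedule says "Study visit 2 will occur 1-6 weeks after the screening visit", that is 7-42 days. If enrollment means the screening visit, the biopsy falls after screening by:
- Phase I (at Visit 2): 7-42 days
- Phase II (24 hours after dosing): 7 + 1 = 8 to 42 + 1 = 43 days
- Phase III (after 10 days of dosing): 7 + 10 = 17 to 42 + 10 = 52 days

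On that reading the window closes before every biopsy. If enrollment means Visit 2, only the Phase I biopsy sits at the end of the window. On either reading 4(c) decides who may enter and does not govern conduct before sampling.

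**2. How long before biopsy does the intercourse request run?**
- Phase II: 3 days + 24 hours = about 4 days
- Phase III: about 10 days, or 10 + 3 = 13 with the lead-in of inclusion 9
- Phase I: no product and no pre-biopsy request in the visit text; only the general duration-of-study wording of inclusion 9 applies

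**3. Which exposures does each provision reach before biopsy?**

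| Provision | Sex-related douching or lubricant | Non-sexual rinse or rectal product |
|---|---|---|
| Abstinence from intercourse | Indirectly | No |
| No enema or preparation (clinic procedure) | Not clearly | Not clearly, if done at home |
| Nothing inserted for 7 days | No (post-biopsy only) | No (post-biopsy only) |
| Exclusion 4(c) | No (entry rule; exempts it) | No (entry rule) |

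The right-hand column contains no clear pre-biopsy provision.

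**4. Illustrative size for swab-collected secretions.** Assumptions, none from the documents: 20% of men rinse; dilution d is 2- or 10-fold; levels are otherwise log-normal with CV 100%, so the log variance is ln(1 + 1²) = 0.693 and the SD is 0.833.

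The SAP reports medians. The log-scale median m of the mixture solves 0.8·Φ(m/0.833) + 0.2·Φ((m + ln d)/0.833) = 0.5.
- d = 2: m = -0.131, ratio e^m = 0.877, a fall of 12%
- d = 10: m = -0.261, ratio 0.770, a fall of 23%

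The large-sample standard error of the log-scale median is 1/(2·f(m)·√n), where f is the density at the median. Without rinsing f = 0.479.
- d = 2: f = 0.455; 0.479/0.455 = 1.05, so the standard error rises 5%
- d = 10: f = 0.370; 0.479/0.370 = 1.30, so it rises 30%; relative efficiency is (0.370/0.479)² = 0.60

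This model covers dilution of secretions only. It says nothing about biopsy tissue or about inflammation caused by a product.

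**The case against.** The strongest reply is that sex-related exposure is already addressed. Inclusion 9 requires willingness to avoid receptive intercourse throughout the study, the Phase II and III visit texts repeat the request, and the risk section gives limiting douching and lubricants as the reason. That stands. A reader might infer that nothing restricts these exposures, and the documents do not support that.

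A reader might also take exclusion 4(c) as licence to douche before biopsy, or as a contradiction of the risk section. It is neither. It is a screening rule, and its exemption is for products used for sex, which suits a population required to report recent receptive intercourse. The rinse at issue here is not sexual use.

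Nor can one say that nothing is recorded. The case report forms are not in the documents, behavioral data are collected, and the risk section has high-risk behavior monitored at visits. The supportable statement is that no item on rectal rinsing or product use is named.

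It is also fair to say that no passage shows rinsing lowers measured drug or cytokines, or that men in this trial would rinse. The reference list includes a study whose title reports epithelial damage in the distal colon from hyperosmolar lubricant, but a title about lubricant is not evidence about rinsing. The mechanism is plausible and unquantified.

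Finally, the arms are randomized and have the same procedure, so noise is likelier than between-arm bias. Cross-phase comparisons would be affected only if rinsing differed by phase. The different abstinence wording makes that possible and does not establish it.

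**Conclusion.** The concern holds in a limited form. The protocol states an aim for the rectal mucosa and pursues it only indirectly. It gives no participant instruction on non-sexual rinsing or rectal products before biopsy, and neither document names an item recording last use. The consequence is possible unrecorded noise in specimens taken once per phase, and possible distortion of cross-phase comparisons if the habit differs between phases.

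The size cannot be computed from the documents. On the assumed inputs, the median in secretions falls 12-23% and its standard error rises 5-30%. A reader working with a geometric mean and log-scale SD could infer that the tenfold case is like losing more than half the men: the log variance becomes 0.693 + 0.2 × 0.8 × (ln 10)² = 1.54, and 0.693/1.54 = 0.45. That is not the summary the SAP reports. For the median the relative efficiency is 0.60, a loss of about 40%, and only at the extreme of an assumed range; at twofold dilution the loss of precision is small.

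This is a minor point of trial conduct. It merits action because the change is simple and an analyst could not make up for it later.

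**What to change.** 1. In the Protocol's Study visits text for Phase I Visit 2, Phase II Visit 3 and Phase III Visit 4, add a pre-biopsy instruction to avoid douching, enemas, rectal lubricant and other rectal products. State one window in identical terms for all three phases. The 3 days already used in inclusion 9 and Phase II is one candidate, counted back from the biopsy. Linking the window to the existing abstinence days would not work, because those differ by phase.
2. Before sampling at the biopsy visit, ask for and record the type and time of last rectal use.
3. In the SAP, add a sensitivity analysis of the rectal endpoints without men reporting use in that window. Keep it secondary, because use is a post-randomization event.

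The cost is one instruction, one form item and a smaller sample in the sensitivity analysis only. With 20 men per arm in Phases II and III and the protocol's 20% non-completion, about 16 remain; if 20% of those reported use, about 3 (16 × 0.2 = 3.2) would be set aside per arm. No dose, visit or sample size changes.

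If specimens have already been collected, last use cannot be reliably recovered, and the report should state this as a limitation.
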